5.6.4	Subgroup Analyses	24
5.6.5	Sensitivity Analyses	24
5.7	Safety Analyses	25
5.7.1	Adverse Events	25
5.7.2	Clinical Laboratory Tests	25
5.7.3	Physical Examination	25
5.7.4	Vital Signs	26
5.7.5	Electrocardiogram	26
5.8	Pharmacokinetic Analyses	26
5.9	Changes to Planned Analysis	26
6.	References	27
7.	Appendix 1	28

Abbreviations

Abbreviation	Term
AE	Adverse Event
ALAT	Alanine Transaminase
ALP	Alkaline Phosphatase
ANCOVA	Analysis of Covariance
ASAT	Aspartate Aminotransferase
ATC	Anatomical Therapeutic Chemicals
CI	Confidence Interval
CBR	Clinical Benefit Rate
CR	Complete Response
CRP	C-reactive protein
DLT	Dose Limiting Toxicity
DSMB	Data and Safety Monitoring Board
FAS	Full Analysis Set
HDL	High Density Lipoprotein
IAP	Interim Analysis Plan
iBOR	Immune Best Overall Response
iCBR	Immune Clinical Benefit Rate
ICH	International Conference on Harmonization
iCPD	Immune Confirmed Progressive Disease
iCR	Immune Complete Response
IMP	Investigational Medicinal Product
iPR	Immune Partial Response
iRECIST	Immune Response Evaluation Criteria in Solid Tumours
iSD	Immune Stable Disease
iUPD	Immune Unconfirmed Progressive Disease
LLOQ	Lower Limit Of Quantification
LSmeans	Least Square Means
Max	Maximum
MedDRA	Medical Dictionary for Regulatory Activities
Min	Minimum
N	Number of observations
Nmiss	Number of Missing Observations
ORR	Overall Response Rate
OS	Overall Survival
OTC	Over-the-counter
PFS	Progression Free Survival
PD	Progressive Disease
PR	Partial Response
PT	Preferred Term
RBC	Red Blood Cells
RECIST	Response Evaluation Criteria in Solid Tumours
RP2D	Recommended Phase 2 Dose
SAE	Serious Adverse Event
SAP	Statistical Analysis Plan

SD	Stable Disease
SOC	System Organ Class
SD	Standard Deviation
SRC	Safety Review Committee
TEAE	Treatment Emergent Adverse Event
TLF	Tables Listing Figures
WBC	White Blood Cells

1. Introduction

This Statistical Analysis Plan (SAP) provides a detailed and technical description of the planned statistical evaluation of the Medivir study BPT-201: “A Phase 1/2, Multicenter, Single-Arm, Open-Label, Dose-Escalation Study of Birinapant in Combination with Pembrolizumab (KEYTRUDA™) in Patients with Relapsed or Refractory Solid Tumors”. The study consists of two phases, a dose-escalation phase followed by a dose-expansion phase.

Mock-up TFLs and an analysis plan for the exploratory objectives regarding biomarkers will be provided in separate documents.

Details regarding the investigational plan, patient selection criteria, dose administration, and schedule of assessments are given in the Clinical Study Protocol (CSP) ”BPT-201 v4.0/incl amendment 03”.

2. Study Objectives

2.1 *Study Objectives Dose Escalation Phase*

2.1.1 *Primary Objective*

To determine the safety and tolerability of the recommended phase 2 dose (RP2D) of birinapant when given in combination with pembrolizumab IV.

2.1.2 *Secondary Objective*

To assess preliminary efficacy of the combination of pembrolizumab and birinapant in patients with relapsed or refractory cancer by effects on tumor size as measured by imaging (CT or MRI) assessed by RECIST 1.1.

2.1.3 *Exploratory Objectives*

1. To assess preliminary efficacy of the combination of pembrolizumab and birinapant in patients with relapsed or refractory cancer by effects on tumor size as measured by imaging (CT or MRI) assessed by iRECIST.
2. To determine the pharmacodynamic markers of birinapant and of pembrolizumab when given in combination at the schedule and dose as defined by the protocol, to include but not to be limited to mechanism of action (inhibition of cIAP1), and of immune surveillance and activation.
3. To assess biomarkers that might predict for responders to the combination treatment and allow comparison to known potential predictive biomarkers of pembrolizumab response.
4. To evaluate birinapant pharmacokinetics in plasma when administered in combination with pembrolizumab.

2.2 *Study Objectives Dose Expansion Phase*

2.2.1 *Primary Objective*

The primary objective in each of the cohorts is as follows:

1. To determine whether the combination of pembrolizumab and birinapant has sufficient antitumor activity, as assessed by ORR, against colorectal cancer to warrant more extensive development.

2. To determine whether the combination of pembrolizumab and birinapant has sufficient antitumor activity, as assessed by ORR, against ovarian cancer to warrant more extensive development.
3. To determine whether the combination of pembrolizumab and birinapant has sufficient antitumor activity, as assessed by ORR, against cervical cancer to warrant more extensive development.
4. To determine the safety and tolerability of the RP2D of birinapant when given in combination with pembrolizumab to patients in the various solid tumors cohort

2.2.2 *Secondary Objectives*

1. To assess the safety and tolerability of the combination of pembrolizumab and birinapant; Overall and in the defined tumor types, colorectal cancer, ovarian cancer and cervical cancer.
2. To assess clinical activity of the combination of pembrolizumab and birinapant in the defined tumor types by effects on tumor response, including CBR, time to response and duration of response, assessed by RECIST 1.1
3. To assess clinical activity of the combination of pembrolizumab and birinapant in the defined tumor types by effect on overall survival
4. To assess clinical activity of the combination of pembrolizumab and birinapant in the defined tumor types by effect on progression free survival.

2.2.3 *Exploratory Objectives*

1. To assess clinical activity of the combination of pembrolizumab and birinapant in the defined tumor types by effects on tumor response, including: CBR, time to response, duration of response, iBOR, duration of iBOR and time to iCPD, assessed by iRECIST.
2. To assess the pharmacodynamic markers of birinapant and of pembrolizumab when given in combination at the schedule and dose as defined by the protocol, to include but not to be limited to mechanism of action (inhibition of cIAP1), and of immune surveillance and activation.
3. To determine biomarkers that might predict for response and/or indicate response to the combination treatment and allow comparison to known potential predictive biomarkers of pembrolizumab response.
4. To evaluate birinapant pharmacokinetics in plasma when administered in combination with pembrolizumab.

3. Study Details

Details of the study design, inclusion/exclusion criteria applicable to the dose escalation phase and for each tumor type of the dose expansion phase are given in the CSP.

3.1 *Study Design and Study Population*

This is a phase 1/2, multicenter, single-arm, open-label, dose-escalation, safety, tolerability, pharmacokinetic and pharmacodynamic study of birinapant and pembrolizumab, conducted in male and female patients, ≥ 18 years of age, who have relapsed or refractory solid tumors.

The study will have two parts, one dose escalation part followed by a dose-expansion phase.

3.1.1 *Dose-escalation phase*

The dose escalation part employs a sequential group dose-escalation design to determine the dose-limiting toxicity (DLT) and recommended phase 2 dose (RP2D) of birinapant administered in combination with pembrolizumab, both administered as a 30-minute

intravenous (IV) infusion. Pembrolizumab will be administered first on Day 1. The birinapant infusion will begin 30 minutes (+10 minutes) following the completion of the pembrolizumab infusion on Day 1. An additional dose of birinapant only will be administered on Day 8. The dose levels of birinapant and pembrolizumab are outlined in Table 1.

Table 1 Dose Escalation Schedule

Dose-Escalation Schedule	
Dose Level	Pembrolizumab + Birinapant (per 21-day cycle)*
Level -1	200 mg pembrolizumab on Day 1 + birinapant 2.8 mg/m²/week on Days 1 and 8
Level 1	200 mg pembrolizumab on Day 1 + birinapant 5.6 mg/m²/week on Days 1 and 8
Level 2	200 mg pembrolizumab on Day 1 + birinapant 11 mg/m²/week on Days 1 and 8
Level 3	200 mg pembrolizumab on Day 1 + birinapant 17 mg/m²/week on Days 1 and 8
Level 4	200 mg pembrolizumab on Day 1 + birinapant 22 mg/m²/week on Days 1 and 8

*Note: A week without treatment (i.e., Days 15-21) will follow the second week of treatment, immediately after which the next 21-day cycle commences.

A minimum of 3 and up to 6 evaluable patients will be enrolled per dose level. For patients enrolled in Dose Level 1, the birinapant starting dose will be 5.6 mg/m²/week. Dose escalation of birinapant will occur in up to three steps. The Safety Review Committee (SRC) will review all the cumulative safety data up to and including completion of Day 21 for the last patient in a cohort from that treatment group prior to dose escalation. Upon review of the safety data the SRC will determine whether or not the safety data supports dose escalation to the next sequential dose level. If the first dose level (5.6 mg/m²) is deemed intolerable, defined as ≥ 2 patients from 3-6 experiencing a DLT, the SRC may decrease the starting dose of the next dosing cohort to 2.8 mg/m² (dose level -1).

If 1 of the 3 to 6 patients enrolled at a given dose level experiences a DLT, enrollment at the next dose level will proceed, if the next highest dose has not already been declared intolerable. However, if 1 of these 3 to 6 patients experiences a DLT at the given dose level and the next highest dose has already been declared intolerable, a minimum of 6 patients are to be enrolled at the given level and the dose at the given level may be the RP2D. A separate safety review will be performed by the SRC to determine the RP2D of the combination of birinapant and pembrolizumab and to begin the dose-expansion phase of the study.

3.1.2 Dose expansion phase

Once the RP2D of birinapant combined with pembrolizumab is defined, additional patients with relapsed or refractory carcinoma will be enrolled in the dose-expansion phase of the study.

Table 2. Dose Expansion Phase

Pembrolizumab + Birinapant (per 21-day cycle)*
200 mg pembrolizumab on Day 1 + birinapant at the RP2D mg/m²/week on Days 1 and 8

The dose expansion phase will comprise of four patient cohorts defined as follows:

- Colorectal cancer (28 patients)

- Ovarian cancer (27 patients)
- Cervical cancer (26 patients)
- Various solid tumors (30 patients, including 5 patients with each of the following 6 tumor types: Small cell lung cancer; Cholangiocarcinoma; Gastroesophageal carcinoma; Mesothelioma; Head and Neck Squamous Cell Carcinoma (HNSCC)-checkpoint inhibitor-naïve; and HNSCC checkpoint inhibitor-experienced)

Predefined interim analyses for futility and safety will be conducted in each of the three main cohorts, i.e. in colorectal cancer, ovarian cancer and cervical cancer, to limit undue exposure before further inclusion into a given cohort. The design of the various solid tumors cohort will limit undue exposure in any of the selected tumor types by virtue of the fact that it limits the number of enrolled patient to five in each tumor type

3.1.3 Study Flow Chart

An overview of the study including the different periods (screening, baseline visit, treatment period and follow-up period) overview of the time points of measurements for each assessment are given in Table 5 (Schedule of Study Procedures and Assessments) in Appendix 1.

3.2 Randomization and Blinding

This study is an open-label study, no randomization and blinding are needed.

3.3 Number of Patients

3.3.1 Sample Size Calculation

3.3.1.1 Dose escalation phase

No formal sample size or power calculations will be performed for the dose-escalation phase of the study. A sample size of 3 to 6 patients per cohort is a feasible sample size to assess safety for dose escalation and dose-limiting toxicity.

3.3.1.2 Dose expansion phase

The dose expansion phase will comprise 4 cohorts of 26-30 patients, as follows:

1. Colorectal cancer (28 patients will be recruited)
2. Ovarian cancer (27 patients will be recruited)
3. Cervical cancer (26 patients will be recruited)
4. Various solid tumors (30 patients will be recruited, including 5 patients with each of the 6 following tumor types: (Small cell lung cancer; Cholangiocarcinoma; Gastroesophageal carcinoma; Mesothelioma; Head and Neck Squamous Cell Carcinoma (HNSCC)-checkpoint inhibitor-naïve; and HNSCC checkpoint inhibitor-experienced)

A Simon's 2-stage design (Simon 1989) will be used for each of the cohorts in colorectal cancer, ovarian cancer and cervical cancer, as outlined in Table 4. A predefined interim analysis allowing stopping each of these cohorts for futility and safety will be conducted in the first stage to limit undue exposure before further inclusion into a given cohort.

The interim analyses will be based on at least 6 and most 13 patients having completed from 9 up to 27 weeks of treatment (3 to 9 cycles) in the colorectal cancer cohort and based on at least 6 and at most 16 and 15 patients in the ovarian cancer cohort and cervical cancer cohort, respectively.

The Simon's two-stage design as outlined in Table 4 yields a type I error rate of 0.05 and statistical power of 0.80 for each of the three main cohorts described above using a one-sided test when the true response rate is 20% for colorectal cancer, 25% for ovarian cancer and 30% for cervical cancer. No formal sample size or power calculation will be performed for the fourth cohort.

Note that one additional patient will be included in each cohort compared to what is stated in Table 4. This patient will only be included in the interim analysis in case a patient drops out in that cohort. Thus, the number of included patients in each cohort will be 27+ 1 (CRC), 26+1 (ovarian) and 25+1 (cervical). In all cases this extra patient will be included in the main/end analysis. If the predefined level for success in a given cohort is reached prior to the stipulated number of patients being enrolled/completed, enrollment in that cohort may be discontinued.

4. Assessments

An overview of the time points of measurements for each assessment is given in Table 5 (Schedule of Study Procedures and Assessments) in Appendix 1.

4.1 *Disposition and Other Supporting Assessments*

4.1.1 *Patient Compliance*

Investigational product will be administered as an IV infusion by study staff and administration information will be recorded in the appropriate CRF. There will be no self-administration of investigational product by the study patients.

4.1.2 *Protocol Deviations*

Protocol deviations will be classified into minor and major and logged as described in the Protocol Deviation Plan.

4.1.3 *Demographic and Baseline Characteristics*

Demographic and baseline characteristics will be collected at the screening visit and will include age, gender, ethnicity, race, height, weight and body surface area.

4.1.4 *Medical History*

A complete medical history will include evaluation for past or present cardiovascular, respiratory, gastrointestinal, renal, hepatic, neurological, endocrine, metabolic, lymphatic, hematologic, immunologic, dermatologic, psychiatric, and genitourinary disorders, medication and surgical history, and review of any other diseases or disorders

4.1.5 *Prior and Concomitant Medications*

Prior medication is defined as medication stopped prior to baseline.

Concomitant medication refers to medication, or therapy, other than the study medication, taken during the study treatment period.

All prescribed drugs, herbal products, vitamins, minerals, and OTC medications are regarded as prior/concomitant medications.

Concomitant therapy or medication usage will be monitored throughout the study.

4.1.6 Eastern Cooperative Oncology Group-Performance Status

Eastern Cooperative Oncology Group Performance (ECOG) Status will be assessed throughout the study.

4.2 Efficacy Endpoints

Details of the assessment of efficacy endpoints are given in Section 9 in the CSP. Definitions of the endpoints are given in Section 4.2.3.

4.2.1 Dose Escalation Phase

4.2.1.1 Primary Efficacy Endpoint

The primary objective of the dose escalation phase concerns safety and tolerability.

4.2.1.2 Secondary Efficacy Endpoints

Tumor response and progression evaluated using RECIST v 1.1

Measures defined by the ORR, will be assessed through RECIST v 1.1 until response or progression and will be subsequently analyzed through iRECIST as an exploratory endpoint (see below).

4.2.1.3 Exploratory Efficacy Variable

Tumor response and progression evaluated using iRECIST.

- a) iBOR
- b) Duration of iBOR
- c) Time to iCPD

Efficacy, as defined by the ORR, will be assessed through RECIST v 1.1 until response or progression and will be subsequently analyzed through iRECIST (iCR, or iPR or iSD or after iUPD iCR, iPR or iSD or iCPD). iBOR will also be assessed.

Overall survival will also be assessed.

4.2.2 Dose Expansion Phase

4.2.2.1 Primary Efficacy Endpoint

The primary endpoint in each of the three main cohorts is as follows:

1. The overall response assessed through RECIST v.1.1 until response or progression in colorectal cancer
2. The overall response assessed through RECIST v1.1 until response or progression in ovarian cancer
3. The overall response assessed through RECIST v1.1 until response or progression in cervical cancer

The primary objective for the cohort with various tumor types concerns safety and tolerability of the RP2D dose of birinapant when given in combination with pembrolizumab.

Measures of tumor response will be evaluated using RECIST v1.1 until response or progression and will be subsequently analyzed through iRECIST as an exploratory endpoint (see below).

4.2.2.2 Secondary Efficacy Endpoints

Clinical Activity: Tumor response will be assessed in all four cohorts by monitoring:

- Progression Free Survival (PFS)
- Clinical Benefit Rate (CBR) defined as CR+PR+SD
- Time to response
- Duration of response
- Overall Survival (OS)

Measures of tumor response will be evaluated using RECIST v1.1 until response or progression and will be subsequently analyzed through iRECIST as an exploratory endpoint (see below).

4.2.2.3 Exploratory Efficacy Variable

Tumor response and progression evaluated in all four cohorts using iRECIST:

- Overall response
- iBOR
- Duration of iBOR
- Time to iCPD
- Clinical Benefit Rate (CBR) defined as iCR+iPR+iSD
- Time to response
- Duration of response

4.2.3 Definition of Efficacy Endpoints

All patients will have a tumor measurement after cycle 3 (week 9) and subsequently after every third cycle. Measures will be assessed through RECIST 1.1 until whichever of the following occurs first:

- Site-assessed disease progression is documented
- The start of new anti-cancer treatment
- Withdrawal of consent
- Death
- The end of the study

After progression, measures will subsequently be analyzed through iRECIST as an exploratory endpoint.

The outcome of a tumor measurement for RECIST 1.1 is a categorization into one of the following categories:

- CR – Complete Response
- PR – Partial Response
- SD – Stable Disease
- PD – Progressive Disease
- Non-CR/Non-PD
- Not Evaluable

For iRECIST, a tumor measurement is categorized into one of the following:

- iCR
- iPR
- iSD
- iUPD
- iCPD
- Non-iCR/Non-iPD
- Not Evaluable

Note that RECIST 1.1 and iRECIST is equivalent until Progressive Disease (PD).

There will be two RECIST 1.1 and iRECIST categorizations, one made in the clinic and one made by an independent radiologist at MEDIAN Technologies. The categorization by the independent radiologist is the one that will be used in the analyses detailed in this SAP. The categorizations at the clinic will be reported descriptively as pure explorative purpose.

A tumour measurement may consist of scans conducted at different days (during the visit window) but there will be only one date associated to the categorization for each visit. That date will be set by the independent radiologist and will be the date used in the derivation of the time to event endpoints below. The overall process for image receipt, review and reporting conducted by MEDIAN Technologies is detailed in the Imaging Review Charter -01, dated 7 February 2018.

4.2.3.1 Overall response (and ORR) assessed through RECIST 1.1

The primary endpoint in the dose expansion phase is the overall response assessed through RECIST v.1.1 until response or progression. A patient with a best overall response of either CP or PR is defined as a patient with an overall response according to RECIST 1.1. A tumor measurement categorized as CP or PR needs a confirmed response of either CP or PR at least 4 weeks after the initial response assessment to be classified as best overall response CP or PR. Examples of patients with an overall response are the following (observations in cycle 3 (week 9) and subsequent every 3rd cycles (9 weeks between each measurement)):

- SD, SD, PR, PR, ; SD, SD, PD (overall response as PR in cycle 9 which is confirmed in cycle 12 (9 weeks after))
- SD, SD, SD, CR, CR (overall response as CR in cycle 12)

Example of patients with no overall response as assessed through RECIST 1.1:

- SD, SD, SD, SD, SD, SD, SD, SD, SD
- SD, PD(iUPD), iSD, iSD, iCPD
- SD, PD(iUPD), iSD, iSD
- SD, SD, PR, SD, SD, PD (PR in cycle 9 is not confirmed)
- SD, PD(iUPD), iPR, iSD, iSD (no overall response according to RECIST 1.1)

The overall response rate (ORR) is defined as the proportion of patients that are classified as overall responders assessed through RECIST 1.1 as described above.

4.2.3.2 Progression Free Survival (PFS)

The PFS is defined as the length of time from the start of treatment the patient lives and does not progress (PD as assessed by RECIST 1.1). Patients who do not die or progress will be censored at the date “last known to be alive”, i.e. the latest date of contact with the patient based on all collected evaluation dates.

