6.3.2 Disease Progression Follow up Visit

Those patients that are discontinued from study treatment due to reasons other than disease progression, but have not withdrawn consent to be followed for survival; will need to be followed every 30 days until documentation of disease progression or initiation of a new therapy for their disease. Once there is documentation of disease progression or initiation of a new therapy for their disease, the patient will move into the long-term survival follow up phase of the study.

The following procedures will be performed at this follow up visit:

- Hematology, serum chemistry
- ECOG PS
- Radiological tumor assessment (RECIST v1.1 and iRECIST) until documentation of disease progression as defined by RECIST or iRECIST
- Initiation of any new cancer therapy and type of therapy

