6.3.3 Overall Survival Follow up Visit

Patients will be monitored by telephone every 3 months for the following:

- Survival status
- Date of next cancer therapy and type of therapy. Participation in any other interventional clinical study during follow-up is permitted.

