- For a **clinically stable** subject with first radiologic evidence of progressive disease by RECIST 1.1 (i.e., **unconfirmed progression of disease or iUPD**), it is at the discretion of the site investigator to continue treating the subject with the assigned treatment per protocol until progression of disease (iCPD) is confirmed at least 28 days from the date of the scan first suggesting PD. If radiologic progression is confirmed by subsequent scan then the subject will be discontinued from trial treatment. If radiologic progression is not confirmed by iRECIST per the site, then the patient should resume or continue trial treatment and have their next tumor imaging according to the protocol schedule of every 9 weeks (end of every 3rd treatment cycle) until progression is confirmed at a later timepoint by the site. In applying iRECIST, the appropriate documentation at

each time point must be made (i.e. iSD, iUPR, iUCR). For a more comprehensive and detailed account of the application of RECIST 1.1 and iRECIST for in-study imaging assessments please refer to the imaging guide document Note that RECIST 1.1 must always serve as the primary imaging assessment guide up to the first indication of disease progression after which iRECIST may be used as described.

- Any subject deemed **clinically unstable** should be discontinued from trial treatment at 1st radiologic evidence of PD and is not required to have repeat imaging for PD confirmation.
- In subjects who discontinue study therapy without documented disease progression, every effort should be made to continue monitoring their disease status by tumor imaging using the same imaging schedule used while on treatment (every 9 weeks), until (1) the start of new anti-cancer treatment, (2) disease progression (3) death, or (4) the end of the study, whichever occurs first.

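### PFS is censored at last contact with no new-therapy rule, so unscanned time counts as progression-free; separately, Kaplan-Meier time to response treats progression and death as ordinary censoring

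*SAP*

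**What the plan says.** **PFS.** SAP 4.2.3.2 runs PFS from start of treatment to death or RECIST 1.1 progression. Otherwise, "Patients who do not die or progress will be censored at the date" last known alive, "i.e. the latest date of contact with the patient based on all collected evaluation dates". It does not mention new therapy. OS (SAP 4.2.3.6) uses the same last-known-alive date but adds the survival telephone calls, which the PFS text does not mention.

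**Who calls progression, and when scanning ends.** SAP 4.2.3: "The categorization by the independent radiologist is the one that will be used in the analyses detailed in this SAP". RECIST 1.1 measurement nevertheless stops at the first of several events, including site-assessed progression and "The start of new anti-cancer treatment".

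**After stopping drug.** Protocol 6.3.2 keeps following patients who stop without progression, with imaging, "until documentation of disease progression or initiation of a new therapy for their disease". After that there is only a three-monthly telephone contact, which records "Date of next cancer therapy and type of therapy" (Protocol 6.3.3). Under Protocol 9.1.5, if site progression in a clinically stable patient is not confirmed, "then the patient should resume or continue trial treatment and have their next tumor imaging according to the protocol schedule of every 9 weeks". A clinically unstable patient "should be discontinued from trial treatment at 1st radiologic evidence of PD and is not required to have repeat imaging for PD confirmation".

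**Neighbouring endpoints.** SAP 4.2.3.5, 4.2.3.9, 4.2.3.10 and 4.2.3.13 censor at the last tumor assessment. Sections 4.2.3.9 and 4.2.3.13 also have a new-therapy rule.

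**Time to response.** SAP 4.2.3.4 and 4.2.3.12 censor every non-responder at the last tumor assessment. SAP 5.3 applies Kaplan-Meier to the time-to-event endpoints of 4.2.3 and reports the plot and the median.

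**The concern.** Progression status is known only up to the last scan, so a last-alive date suits OS but not PFS. Take a patient with stable disease at week 9, new therapy at week 10 and last contact at week 52. PFS is censored at 52 weeks, of which 43 had no scan; under the SAP's own convention for the other durations it would be 9 weeks.

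The exposed group is limited: mainly patients who start new therapy without centrally read progression, and clinically unstable patients with a site progression that the central reader does not call.

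Time to response has a different fault. A patient who has died or progressed under RECIST 1.1 can no longer become a RECIST responder. Kaplan-Meier censoring treats that patient as if a response were still to come.

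At stake are secondary curves in all four cohorts of a single-arm study, where readers will compare PFS with outside data. The response curve could also disagree with the ORR in the same report.

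**Working it through.** The plan states no PFS or time-to-response figure to reproduce, so this is an illustration.

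**PFS inputs.** Median PFS 1.9 months (used as time to progression) and OS 13.1 months (Protocol 1.5.2, pembrolizumab alone); scans every 63 days, that is at 2.07, 4.14 and 6.21 months. Assumed: exponential, independent times; a share f of patients alive without progression leaves imaging at week 9; f = 10/20/30% is not in the documents.

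1. Alive without progression at week 9: 2^(−2.07/1.9) × 2^(−2.07/13.1) = 0.470 × 0.896 = 0.421. Leavers are 4/8/13% of the cohort, about 1, 2 or 3 of 27.
2. Six-month PFS with full scanning: 2^(−4.14/1.9) × 2^(−6/13.1) = 0.221 × 0.728 = 0.161. Given week-9 status: 0.161/0.421 = 0.382.
3. Under the SAP rule only death ends a leaver's PFS: 2^(−3.93/13.1) = 0.812.
4. SAP rule overall: 0.421 × [(1−f) × 0.382 + f × 0.812].

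| Six-month PFS | f = 10% | 20% | 30% |
|---|---|---|---|
| Full scanning | 16.1% | 16.1% | 16.1% |
| SAP rule, contact to cutoff | 17.9% | 19.7% | 21.5% |
| SAP rule, contact = visits only | 17.2% | 18.3% | 19.5% |
| Fix, all leavers start therapy | 16.1% | 16.1% | 16.1% |
| Fix, half do | 16.6% | 17.2% | 17.9% |
| Fix, none do | 17.1% | 18.2% | 19.4% |

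The visits-only row and the half and none rows come from simulation (2,000,000 patients per scenario, 24-month cutoff; visits-only censors living leavers 37 days after the last scan). The last row is last-scan censoring with all deaths kept. It splits the excess of 1.8/3.6/5.4 points into 0.8/1.5/2.1 from the censoring date and 1.0/2.1/3.3 from counting late deaths as the event.

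**Median.** PFS drops from 0.896 to 0.421 at the week-9 scan, so the median is 2.1 months under every rule. In simulated cohorts of 27 it changes in 2/3/5%. With assumed medians of 6 and 18 months it steps from 5.6 to 6.2 months at each f.

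**If leavers do badly.** Let f = 20% and assume a 2-month median survival after leaving, so 2^(−3.93/2) = 0.256 survive to six months.
- Full scanning: 0.421 × (0.8 × 0.382 + 0.2 × 0.470 × 0.256) = 13.9%.
- SAP rule: 0.421 × (0.8 × 0.382 + 0.2 × 0.256) = 15.0%.
- Fix, all starting therapy: 0.421 × 0.382 = 16.1%.

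**Time to response.** Assume a true ORR of 20%, responses split 60/30/10% over scans 1 to 3, and half of the remaining non-responders progressing at each scan. The sets at risk are 1, 0.40 + 0.08 = 0.48 and 0.20 + 0.02 = 0.22:

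1 − (1 − 0.12/1)(1 − 0.06/0.48)(1 − 0.02/0.22) = 30%.

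With 30/50/70% progressing per scan, the result is 24/30/44% for this split and 22/25/34% for an 80/15/5% split (middle value: 1 − 0.84 × (1 − 0.03/0.44) × (1 − 0.01/0.21)).

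If all responses fall at scan 1, deaths before it still matter. SAP 5.2.2 keeps those patients in the set, but their last tumor assessment is baseline, so they are not at risk at week 9: 0.20/0.896 = 22.3%.

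**The case against.** The strongest reply is that little that is reported would change. SAP 5.3 plans a plot and a median, the median does not move in the document-based illustration, and every time-to-response scenario above peaks below 50%, so that median is not reached either way. SAP 5.4.4 plans no inference on secondary endpoints. This stands and limits the weight of the point, but the plotted curves would still be wrong.

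Second, the direction can be disputed. Against full scanning it is upward: with contact kept to death or cutoff, a leaver's event can only be recorded later. Against the fix it is not fixed. In the poor-prognosis case the fix gives 16.1%, further from 13.9% than the SAP rule's 15.0%. This stands, and it is why a sensitivity analysis is needed. The fix also leaves the late-death effect in leavers who start no therapy.

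Third, contact may exclude telephone calls in 4.2.3.2. The date effect then almost vanishes and the late-death effect stays.

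Fourth, some cover exists. SAP 5.2.2 counts death or an adverse-event stop before the first assessment as progression, and the imaging charter, which is not available here, may address site and central disagreement.

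Stronger readings that a reader might infer are not supported:
- That everyone off drug goes unscanned: Protocol 6.3.2 and 9.1.5 continue imaging.
- That median PFS is inflated by months: in this setting that needs many patients to leave around or before the first scan. The documents give no such share, and SAP 5.2.2 excludes most patients without a post-baseline assessment.

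**Conclusion.** The point holds and should be fixed. SAP 4.2.3.2 applies an OS-type censoring date to a scan-based endpoint, without a new-therapy rule and against the SAP's own convention for durations. Relative to full scanning, PFS is biased upward: about 2 to 5 points at six months in the ovarian illustration, with no shift in the median. That size rests on assumed leaving shares, exponential times, leaving unrelated to prognosis, and contact continuing to the cutoff.

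Separately, 1 − Kaplan-Meier overstates the probability of response whenever non-responders leave the risk set before others respond. This includes deaths before the first scan, so it can happen even if every response is at week 9.

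PFS and time to response are secondary, the immune version is exploratory, and all are descriptive. It would be wrong to infer that the cohort go/no-go decisions are compromised: the primary ORR test uses neither endpoint.

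**What to change.** 1. **SAP 4.2.3.2.** Censor patients without centrally read progression or death at the last evaluable tumor assessment. Censor those who start new anti-cancer therapy without prior progression at the last tumor assessment before it, adapting 4.2.3.9 and 4.2.3.13. Keep the 5.2.2 rule, and keep the last-known-alive date for OS. Add a sensitivity analysis that counts new therapy and later deaths as events. State how palliative radiotherapy is handled, since Protocol 5.6.1 treats it as clinical progression. The same new-therapy sentence could go into 4.2.3.5 and 4.2.3.10, which lack it.
2. **SAP 4.2.3.4 and 4.2.3.12.** Summarise time to response in confirmed responders only, or use cumulative incidence with progression (iCPD for the immune version) and death as competing events.

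Cost: a few sentences and one extra analysis. No new data are needed, because the next-therapy date is already collected (Protocol 6.3.3). Reported PFS will usually be slightly less favourable. If leavers have a poor prognosis, the new censoring is informative and can make PFS look better, which the sensitivity analysis is there to show.
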